4.1.2 Definitions

4.1.2.1 Short-term treatment period, long-term extension period, baseline value

The study consists of the following study periods:

- 1) The qualification period. This period starts with enrollment and ends on the start of the lead-in period.
- 2) The 8-week lead-in period. During this period, subjects will optimize their diabetes management based on individual subject challenge to glycemic control. No placebo or study medication will be provided during the lead-in period.
- 3) The 24-week short-term double-blind treatment period which will be the timeframe for the primary efficacy analysis. On the Day 1 visit, subjects who meet all the protocol-specific enrollment and randomization criteria will be randomized. It will be recommended that subjects reduce their daily insulin dose by 20% for both basal and bolus insulin on Day 1 following randomization to reduce the risk of hypoglycemia.
- 4) The 28-week long-term treatment period where additional safety and efficacy measurements will be obtained. After completing the short-term period, subjects will enter the 28-week subject- and site-blinded long-term treatment period.
- 5) The follow-up period. After completing the short-term and long-term period, subjects will enter the 4 week follow-up period.

For each subject, the baseline value of a parameter is defined as the last assessment of that parameter on or prior to the date/time of the first dose of the double-blind study medication.

For measurements referring to 24-hour collection periods (i.e. daily insulin dose), all available data prior to the date of the first dose of the double-blind study medication will be considered as falling in the baseline analysis window.

For measurements referring to multiple data points over the course of a day (i.e. 6-point SMBG measurement parameters and CGM parameters), all available data on or prior to the date/time of the first dose of the double-blind study medication will be considered as falling in the baseline analysis window.

For measurements referring to 24-hour collection periods (i.e. daily insulin dose) and those referring to multiple data collection points over a day (i.e. 6-point SMBG measurement parameters and CGM parameters), for which several values are considered as falling in the

baseline analysis window, the baseline value will be identified using the algorithm outlined in Section 6.3 in order to define the baseline value.

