4.2.3.1 Primary efficacy analysis

The primary endpoint is the change in HbA1c from baseline to Week 24. The comparison between each dapagliflozin group and placebo are of interest for this study.

The primary endpoint is the change in HbA1c from baseline to Week 24. The primary estimand for the treatment difference at Week 24 if subjects did not discontinue randomized treatment. The primary analysis of the change in HbA1c from baseline to Week 24 will be based on a longitudinal repeated measures analysis using 'direct likelihood' (see Section 4.1.6.1). The analysis will include all available data up to Week 24 or until premature discontinuation of randomized treatment, whichever occurs first. The analysis will be conducted regardless of insulin up-titration.

The model will use subjects in the primary efficacy dataset (i.e., Full Analysis Set) who have a baseline assessment and any post-baseline double-blind treatment period assessment.

For subjects whose post-randomization insulin dose is up-titrated by more than 25% of insulin relative to baseline, measurements obtained after the first instance the 25% up-titration criteria

is met will correspond to rescue and be included in the primary analysis but excluded in one of sensitivity analyses.

Point estimates and 95% confidence intervals for the mean change within each treatment group as well as the difference in mean change between each dapagliflozin treatment group and placebo will be calculated. Student t-statistics corresponding to the Type III sums of squares for the differences in the least squares means between each dapagliflozin group and placebo at Week 24 will be calculated.

To assess the robustness of the primary efficacy analysis for the change in HbA1c from baseline to Week 24, additional sensitivity analyses will be carried out using the following approaches:

- A longitudinal repeated measures analysis, similar to the primary analysis, excluding measurements obtained after the first instance the 25% up-titration criteria is met.
- ANCOVA analysis including subjects in the Full Analysis Set who have a baseline assessment and at least one post-baseline assessment using LOCF methodology for Week 24 (see Section 4.1.5.1).
- ANCOVA analysis including subjects in the Full Analysis Set who have a baseline assessment and a Week 24 assessment (i.e. a “completers” analysis, but without LOCF methodology) (see Section 4.1.5.1).

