Change from baseline in seated systolic blood pressure

The change in seated systolic blood pressure from baseline to Week 24 is an exploratory endpoint; therefore no statistical testing will be performed to compare each dapagliflozin group and placebo in subjects with hypertension at baseline.

Seated systolic blood pressure is collected at selected visits during the short-term double-blind treatment period with a single value at each visit.

The analysis of the change in seated systolic blood pressure from baseline to Week 24 will be based on a longitudinal repeated measures analysis using 'direct likelihood' as outlined in Section 4.1.6.1.

The model will be restricted to data from subjects in the primary efficacy dataset (i.e., Full Analysis Set) who have at least one baseline assessment and any post-baseline double-blind treatment period assessment and who have hypertension at baseline (defined as seated SBP \geq 140mmHg and/or seated DBP \geq 90mmHg).

Point estimates and 2-sided 95% confidence intervals for the mean change within each treatment group, as well as the difference in mean change between each dapagliflozin treatment group and placebo, will be calculated.

Time to insulin up-titration more than 25% from baseline

Time to the first post-randomization insulin up-titration by more than 25% relative to the baseline insulin dose will be presented by treatment group using a Kaplan-Meier curve using methodology described in Section 4.1.7. A plot will be presented only when there are at least 5 subjects meeting the criteria in one treatment group. An accompanying table of the cumulative proportion of subjects whose insulin was up-titrated by more than 25% from baseline at specific time points during the short-term double-blind treatment period will be produced.

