- 4) **Probable symptomatic hypoglycemia.** “An event during which symptoms of hypoglycemia are not accompanied by a plasma glucose determination (but that was presumably caused by a plasma glucose concentration $\leq 70\text{mg/dl}$ [3.9mmol/l]). Since many people with diabetes choose to treat symptoms with oral carbohydrate without a test of plasma glucose, it is important to recognize these events as “probable” hypoglycemia. Such self-reported episodes that are not confirmed by a contemporaneous low plasma glucose determination may not be suitable outcome measures for clinical studies that are aimed at evaluating therapy, but they should be reported.” (Workgroup on Hypoglycemia, American Diabetes Association 2005)
- 5) **Relative hypoglycemia.** “An event during which the person with diabetes reports any of the typical symptoms of hypoglycemia, and interprets those as indicative of hypoglycemia, but with a measured plasma glucose concentration $> 70\text{mg/dl}$ (3.9mmol/l). This category reflects the fact that patients with chronically poor glycemic control can experience symptoms of hypoglycemia at plasma glucose levels $> 70\text{mg/dl}$ (3.9mmol/l) as plasma glucose concentrations decline toward that level (27,28). Though causing distress and interfering with the patient’s sense of well-being, and potentially limiting the achievement of optimal glycemic control, such episodes probably pose no direct harm and therefore may not be a suitable outcome measure for clinical studies that are aimed at evaluating therapy, but they should be reported.” (Workgroup on Hypoglycemia, American Diabetes Association 2005)

The above mentioned classification refers to plasma glucose measurements. In cases where whole blood glucose measurements are reported, they will be converted to plasma equivalent as described in section 6.12.

All analyses of hypoglycemic events will be performed both overall and by class of events as per ADA categorization (Workgroup on Hypoglycemia, American Diabetes Association 2005) presented above.

The proportion of subjects with hypoglycemic events will be tabulated by treatment group in the short-term double-blind treatment period, both regardless of insulin up-titration and, separately, including data only prior to the first post-randomization insulin up-titration by more than 25% relative to baseline.

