SAEs of hypoglycemia with an onset during the short-term double-blind treatment period and those leading to discontinuation of study medication will be summarized by treatment group. When summarizing hypoglycemic events leading to discontinuation no upper cutoff day windows are applied. For short-term double-blind period analyses the only upper cutoff date is the start date of the long-term treatment period.

Time to hypoglycemic events leading to discontinuation of study medication will be presented by treatment group using a Kaplan-Meier curve using methodology described in Section 4.1.7. A plot will be presented only when there are at least 5 events in one treatment group. An accompanying table of the cumulative proportion of subjects with time to hypoglycemic

events leading to discontinuation of study medication at specific time points during the short-term double-blind treatment period will be produced.

The number and percentage of subjects with hypoglycemic events will be summarized by frequency of events (recurrence; for severe hypoglycemia: 1, 2, ≥ 3 ; for documented symptomatic hypoglycemia: 1-3, 4-6, or ≥ 7 , for asymptomatic, probable symptomatic, relative hypoglycemia and all hypoglycemic events independently of ADA categorization: 1-5, 6-9, or ≥ 10). The total number of events by treatment group will be summarized for the short-term double-blind treatment period.

The exposure-adjusted incidence rate of hypoglycemic events (including recurrences) will be summarized by monthly intervals in order to assess any over time changes in the incidence rate.

In order to explore any differences in the distribution of hypoglycemic events by randomization strata categories, the proportion of subjects with hypoglycemic events will be summarized for the whole duration of the double-blind treatment period by randomization stratification subgroups. Additionally, this analysis will be repeated by subgroups of change in HbA1c from baseline to Week 24 LOCF (i.e. reduction $\geq 0.5\%$ vs. reduction $< 0.5\%$) and HbA1c week 24 LOCF value (i.e. week 24 LOCF value $< 7\%$ vs. week 24 LOCF value $\geq 7\%$).

A listing of subjects will be produced and it will display all hypoglycemic events with an onset date/time from the start date/time of short-term double-blind treatment period up to the start date of the long-term treatment period.

Hypotension/Dehydration/Hypovolemia

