6.7.2 At event level

At event level, each unique AE record will be counted. Unique AE record can be obtained by collapsing all AE records following a standard algorithm. In addition to frequency summary, exposure adjusted summary will also be provided where the overall exposure of a subject is calculated from first dose day to the last day of short-term treatment regardless of whether a subject has had an event or not.

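### The pre-up-titration hypoglycemia table gives a crude proportion although observation stops at up-titration; a person-time rate cut at the same date should stand beside it

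*SAP*

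**What the plan says.** SAP section 4.2.4.4 (Hypoglycemia) states: "The proportion of subjects with hypoglycemic events will be tabulated by treatment group in the short-term double-blind treatment period". This is done once on all data in that period and once "separately, including data only prior to the first post-randomization insulin up-titration by more than 25% relative to baseline". The same section repeats all hypoglycemia analyses by ADA class, and section 4.2.4 makes the Treated Subjects data set the basis of every safety summary. No separate denominator is given for the truncated table.

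Up-titration is defined in section 4.1.2.4 and dated to the first day of the first qualifying 14-day window, with windows starting at the first dose. Section 4.2.3.1 treats it as a rescue event for efficacy: later HbA1c values "is met will correspond to rescue and be included in the primary analysis but excluded in one of sensitivity analyses".

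Four other provisions bear on the point:
- Section 4.2.4.4: "The exposure-adjusted incidence rate of hypoglycemic events (including recurrences) will be summarized by monthly intervals". These rates are not tied to the pre-up-titration data.
- Section 6.7.2, on event-level adverse event counts: "the overall exposure of a subject is calculated from first dose day to the last day of short-term treatment". This exposure is not cut at up-titration.
- Section 4.2.4.4: "Time to hypoglycemic events leading to discontinuation of study medication will be presented by treatment group using a Kaplan-Meier curve". No other hypoglycemia analysis uses Kaplan-Meier.
- Section 4.2.3.2: "Time to the first post-randomization insulin up-titration by more than 25% relative to the baseline insulin dose will be presented by treatment group".

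**The concern.** A crude proportion compares arms fairly only if subjects are observed for similar lengths of time. Here observation is deliberately stopped at an event that follows randomization and may depend on treatment. A subject up-titrated in week 4 contributes four weeks of risk but, if event-free, counts the same as a subject observed for 24 weeks. If one arm is up-titrated more often or earlier, its proportion falls even when its hazard is identical.

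Hypoglycemia is the first safety objective in section 1.1, so the table will be read. It could show a between-arm difference where there is none, or hide one that exists. The SAP already plans time to first event for genital infection, urinary-tract infection and DKA, but not for the hypoglycemia table whose follow-up is cut on purpose.

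**Working it through.** **Inputs.** The SAP states no figure for this table, so there is none to reproduce. Follow-up is 24 weeks (section 4.1.2.1: "The 24-week short-term double-blind treatment period which will be the timeframe for the primary efficacy analysis"). Arm size is 256 (section 1.3; 243/0.95 = 255.8). The 24-week hypoglycemia risk R and the proportion up-titrated p are assumed. The denominator is taken to be all treated subjects, as section 4.2.4 implies. Both arms have the same true risk, so any gap is an artefact.

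**Model A: constant hazard, up-titration times uniform over 24 weeks.** With L = -ln(1 - R), a subject not up-titrated has an event with probability R. An up-titrated subject has an observed event with probability m = 1 - R/L. The crude proportion is (1 - p)R + p·m.

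- R = 7%: L = 0.0726, m = 0.0354.
  - p = 15%: 0.85 × 0.07 + 0.15 × 0.0354 = 6.5%. p = 5%: 6.8%. Ratio 1.05.
  - p = 30%: 0.70 × 0.07 + 0.30 × 0.0354 = 6.0%. p = 10%: 6.7%. Ratio 1.12.
  - p = 40%: 5.6%. p = 10%: 6.7%. Ratio 1.18 from unrounded values.
- R = 50%: L = 0.6931, m = 0.2787.
  - p = 30%: 0.70 × 0.50 + 0.30 × 0.2787 = 43.4%. p = 10%: 47.8%. Gap 4.4 points.

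**Model B: up-titration also at a constant rate.** With h = -ln(1 - R) and u = -ln(1 - U), where U is the proportion up-titrated by week 24, the crude proportion is h/(h + u) × [1 - exp(-(h + u))].

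| True risk | Gap, U 5% vs 10% | Gap, U 5% vs 30% |
|---|---|---|
| 5% | 0.1 points | 0.7 points (4.9% vs 4.2%) |
| 50% | 1.1 points | 6.0 points (48.9% vs 42.9%) |
| 80% | 1.5 points | 8.1 points (78.5% vs 70.4%) |
| 95% | 1.4 points | 7.4 points (93.6% vs 86.2%) |

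Mean time to the earlier of up-titration and week 24 is 23.4 versus 22.8 weeks at 5% versus 10%, and 23.4 versus 20.2 weeks at 5% versus 30%.

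**Early up-titration.** If all up-titration fell at week 4, 5% versus 30% would give gaps of 1.0, 9.8 and 13.9 points at true risks of 5%, 50% and 95%.

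**Does censoring remove the gap?** Model B was simulated with 400,000 subjects per setting at U = 5% versus 30%. Kaplan-Meier censored at up-titration gave 5.1% versus 5.1%, 50.0% versus 50.0% and 95.0% versus 95.0%. First-event rates per person-time also agreed between arms. This holds because up-titration was simulated independently of hypoglycemia risk.

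**The case against.** The strongest reply is that little depends on this table. It is descriptive, with no test attached, and its companion regardless of up-titration is not cut there. No hypothesis, error rate or estimand uses it. The Kaplan-Meier display of time to up-titration lets a reader see unequal truncation. The distortion can also be small: at a 7% risk and 30% versus 10% up-titrated, the gap of 0.69 points is about 1.8 subjects in 256 (256 × 0.0069), against a standard error of about 2.2 points. The up-titration rule is demanding as well. Every non-missing daily midpoint in a 14-day window must exceed baseline by 25%, and a subject whose dose was first reduced by the full 20% would need 1.25/0.80 = 1.56 times the reduced dose to qualify.

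Most of this stands and limits the weight of the point. It does not remove it. The up-titration curve reveals an imbalance but does not adjust the hypoglycemia table, and the planned monthly rates are not restricted to time before up-titration. For common event classes, a large imbalance moves the proportion by several points.

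The objection is also right that Kaplan-Meier censored at up-titration is not assumption-free. If up-titration is related to hypoglycemia risk, the censoring is informative. That argues for adding to the planned table rather than replacing it.

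**Conclusion.** The point holds as a limited weakness in one descriptive safety table. At equal constant hazard, and with all treated subjects in the denominator, the truncated proportion is lower in the arm up-titrated more. The gap is about 0.1 to 1.5 points at 5% versus 10% up-titrated. It is 0.7 points (7% risk) to 4.4 points (50% risk) at 30% versus 10% under uniform timing. It grows with the imbalance and with earlier up-titration. All these rates are assumed; the SAP gives none.

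A reader might infer more than the SAP supports:
- **That the table works against dapagliflozin.** One may expect placebo subjects to be up-titrated more, but the SAP does not say which arm that will be. The artefact follows the arm with more up-titration, whichever it is.
- **That this is the one table designed to isolate the drug's effect from that of added insulin.** The SAP states no purpose for it.
- **That the planned exposure-adjusted rates run by calendar month.** The SAP says only monthly intervals, to look at change over time.
- **That the hypoglycemia assessment as a whole is compromised.** The analysis regardless of up-titration is not truncated at up-titration.

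**What to change.** In section 4.2.4.4, keep the pre-up-titration proportion and add beside it:

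1. By ADA class, hypoglycemic events per 100 patient-years. Exposure ends at the earlier of the first up-titration above 25% and the end of the hypoglycemia window already defined there (4 days after the last short-term dose, or the start of the long-term period). State that this exposure, not the one in section 6.7.2, applies.
2. For severe hypoglycemia, the Kaplan-Meier cumulative proportion with a first event, censored at up-titration, using the methods of section 4.1.7.

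Name the analysis regardless of up-titration as the main one. Footnote the truncated results: follow-up ends at up-titration, its length may differ by arm, and censoring there may be informative.

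The cost is a short SAP revision, one derived exposure variable and slightly more programming. Section 4.1.2.4 already derives the up-titration date, and event onset dates are already needed to apply the hypoglycemia window. No new data are required.

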1.1 Study objectives

Primary Objective

The primary objective of this study is to compare the change from baseline in HbA1c after 24 weeks of double-blinded treatment with dapagliflozin 5 mg or 10 mg plus adjustable insulin versus placebo plus adjustable insulin.

Secondary Objectives:

Efficacy

Six secondary efficacy objectives are identified for special consideration in this study, in addition to the primary objective:

- Compare the percent change from baseline in total daily insulin dose with dapagliflozin 5 mg or 10 mg plus adjustable insulin versus placebo plus adjustable insulin after 24 weeks of double-blinded treatment
- Compare the percent change from baseline in body weight with dapagliflozin 5 mg or 10 mg plus adjustable insulin versus placebo plus adjustable insulin after 24 weeks of double-blinded treatment
- Compare the change from baseline in the mean value of 24-hour glucose readings obtained from continuous glucose monitoring (CGM) with dapagliflozin 5 mg or 10 mg plus adjustable insulin versus placebo plus adjustable insulin after 24 weeks of double-blinded treatment
- Compare the change from baseline in mean amplitude of glucose excursion (MAGE) of 24-hour glucose readings obtained from CGM with dapagliflozin 5 mg or 10 mg plus adjustable insulin versus placebo plus adjustable insulin after 24 weeks of double-blinded treatment
- Compare the change from baseline in the percent of 24-hour glucose readings obtained from CGM that falls within the target range of > 70 mg/dL and ≤ 180 mg/dL with dapagliflozin 5 mg or 10 mg plus adjustable insulin versus placebo plus adjustable insulin after 24 weeks of double-blinded treatment
- Compare dapagliflozin 5 mg or 10 mg plus adjustable insulin versus placebo plus adjustable insulin for the proportion of subjects achieving an HbA1c reduction from baseline to Week 24 visit $\geq 0.5\%$ without severe hypoglycemia events

Safety

- To assess the proportion of subjects with hypoglycemia events and the frequency and severity of the hypoglycemia events with dapagliflozin 5 mg or 10 mg plus adjustable insulin versus placebo plus adjustable insulin
- To evaluate the safety and tolerability by assessment of adverse events (AE), vital signs, diabetic ketoacidosis (DKA) events, physical examination findings, ECGs, and laboratory values.

Other/Exploratory Objectives:

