- 11) Assess the changes from baseline to Week 24 in the summary score for treatment satisfaction and scores for perceived frequency of hyperglycemia and perceived frequency of hypoglycemia, respectively, as measured by the Diabetes Treatment Satisfaction Questionnaire status (DTSQs) between the dapagliflozin 5 mg or 10 mg plus adjustable insulin versus placebo plus adjustable insulin after 24 weeks of double-blinded treatment
- 12) Compare the number of non-severe hypoglycemic events per subject in those achieving an HbA1c reduction of $\geq 0.5\%$ on dapagliflozin 5 mg or 10 mg plus adjustable insulin versus placebo plus adjustable insulin from baseline to Week 24 visit.
- 13) Assess the change from baseline to Week 24 in the summary score of fear of hypoglycemia as measured by the Hypoglycemia Fear Survey (HFS-II) Worry Subscale between the dapagliflozin 5 mg or 10 mg plus adjustable insulin versus placebo plus adjustable insulin after 24 weeks of double-blinded treatment.

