4.1.8 Proportion of subjects with a pre-defined characteristic at week t

The proportion of subjects with a pre-defined characteristic at Week t will be analyzed using a logistic regression model with adjustments for baseline values and randomization strata when there are at least 5 responders on average by treatment group. This pre-defined characteristic could correspond to a continuous variable dichotomized into a categorical endpoint. The odds ratio in response rate between each of the dapagliflozin treatment groups and the control group will be displayed along with the 2-sided 95% confidence intervals. P-values will be calculated if applicable. When there are less than 5 responders on average by treatment group, the unadjusted (and difference) proportions, exact 95% confidence interval, and p-values from the Fisher's exact test (when applicable) will be provided.

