The analysis of the change in each of the CGM parameters from baseline to Week 24 will be based on a longitudinal repeated measures analysis using ‘direct likelihood’ as outlined in Section 4.1.6.2.

The model will use subjects in the primary efficacy dataset (i.e., Full Analysis Set) who have at least one baseline assessment and any post-baseline double-blind treatment period assessment.

Point estimates and 2-sided 95% confidence intervals for the mean change within each treatment group, as well as the difference in mean change between each dapagliflozin treatment group and placebo, will be calculated. Only for the secondary endpoints, t-statistic corresponding to the Type III sums of squares for the differences in the least squares means

between each dapagliflozin group and placebo at Week 24 will be calculated. No p-value will be estimated for the exploratory analyses.

Proportion of subjects achieving glycemic response

The proportion of subjects having an HbA1c reduction from baseline to Week 24 (LOCF) \geq 0.5% and without severe hypoglycemia events is a secondary combined endpoint.

The proportion will be analyzed using the methodology outlined in Section 4.1.8. The odds ratio and its 2-sided 95% confidence interval between each dapagliflozin treatment group and placebo, will be calculated. The analysis will use subjects in the primary efficacy dataset (i.e., Full Analysis Set) who have at least one baseline assessment and any post-baseline double-blind treatment period assessment.

The proportion of subjects having an HbA1c reduction from baseline to Week 24 LOCF \geq 0.5% and an HbA1c Week 24 LOCF value $<$ 7% are separate exploratory endpoints; therefore no statistical testing will be performed to compare each dapagliflozin group and placebo.

Number of non-severe hypoglycemic events per subject in those achieving a HbA1c reduction of \geq 0.5% from baseline to the week 24 visit (LOCF) is an exploratory endpoint; therefore no statistical testing will be performed to compare each dapagliflozin group and placebo.

Analyses will be analyzed using the methodology outlined in Section 4.1.8 using the randomized subjects dataset and the LOCF visit. No p-value will be calculated. The analysis will use subjects in the primary efficacy dataset (i.e., Full Analysis Set) who have at least one baseline assessment and any post-baseline double-blind treatment period assessment.

Change from baseline in fasting plasma glucose

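### An exploratory count of non-severe hypoglycemic events per subject is assigned to a method for yes/no outcomes, on a dataset the SAP does not define

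*SAP*

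**What the plan says.** **The count endpoint.** Exploratory objective 12 in SAP Section 1.1 reads "Compare the number of non-severe hypoglycemic events per subject in those achieving an HbA1c reduction" of at least 0.5%, for each dapagliflozin dose against placebo. Section 3.4 lists the matching variable. Section 4.2.3.2 repeats it under the heading on glycemic response, together with two genuine proportions (HbA1c reduction of at least 0.5%, and HbA1c below 7%), and rules out statistical testing for all three. The method follows: "Analyses will be analyzed using the methodology outlined in Section 4.1.8 using the randomized subjects dataset and the LOCF visit". The closing sentence of the same paragraph names the Full Analysis Set instead.

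**The method it points to.** Section 4.1.8 begins: "The proportion of subjects with a pre-defined characteristic at Week t will be analyzed using a logistic regression model". It reports odds ratios with 95% intervals. With fewer than 5 responders per group on average, it falls back to unadjusted proportions, exact intervals and Fisher's exact test.

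**The subgroup displays.** In Section 4.2.4.4 (Hypoglycemia), "the proportion of subjects with hypoglycemic events will be summarized for the whole duration of the double-blind treatment period by randomization stratification subgroups". Then: "Additionally, this analysis will be repeated by subgroups of change in HbA1c from baseline to Week 24 LOCF", and likewise by the Week 24 HbA1c value. For whole treatment groups the same section also plans total events, recurrence categories (for example "all hypoglycemic events independently of ADA categorization: 1-5, 6-9" and 10 or more) and a rate: "The exposure-adjusted incidence rate of hypoglycemic events (including recurrences) will be summarized by monthly intervals".

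**The concern.** Events per subject is a count. Section 4.1.8 accepts only a binary outcome, so a programmer who follows the text must either choose a cut after the event or set the instruction aside. The first route yields an odds ratio whose size depends on the cut. The second yields a summary that the plan does not describe.

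Two further gaps sit in the same sentence.

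- Responder status uses LOCF, so a responder may have stopped treatment early and been at risk for fewer days. Section 4.1.8 has no exposure term to allow for this.
- The dataset named is not among those defined in Section 2.1. It also conflicts with the Full Analysis Set named at the end of the paragraph.

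A lesser matter concerns the subgroup tables in Section 4.2.4.4. Their stated purpose is to explore how hypoglycemic events are distributed over the strata, but they show only whether a subject had any event. For classes in which most subjects have several events, that measure can be nearly the same across strata while event rates differ.

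**Working it through.** **Step 1: set the sections side by side.**

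| Item | Section 4.2.3.2 (count endpoint) | Section 4.1.8 (assigned method) |
|---|---|---|
| Outcome | events per subject: 0, 1, 2, ... | characteristic present or absent |
| Time frame | events accrued over the period | status at Week t |
| Unequal follow-up | possible, since responders are defined by LOCF | no exposure term |
| Cut-off | none stated | needed if a count is to be used |
| Result wanted | number per subject | odds ratio or difference in proportions |

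Section 4.1.8 allows a continuous variable to be dichotomized, so a cut count could enter it. But no cut is given anywhere, and the result would no longer be events per subject. No other method for this endpoint appears in the SAP.

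**Step 2: the dataset.** Section 2.1 defines the enrolled, lead-in, full analysis, evaluable and treated sets. None is a randomized-subjects set. Section 9.4, item 3, records that this set was replaced by the Full Analysis Set, so its appearance in Section 4.2.3.2 is leftover text.

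**Step 3: how much an unstated cut could matter.** The SAP gives no hypoglycemia rate, so there is no figure of its own to reproduce. The inputs here are assumptions: negative binomial counts with mean m and dispersion k, and a true rate ratio of 1.25.

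For the cut at 1 or more, P = 1 − (1 + k·m)^(−1/k). With m = 3 and k = 0.5:

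- control: 1 − 2.5^(−2) = 0.840
- at 1.25 × 3 = 3.75: 1 − 2.875^(−2) = 0.879
- odds ratio: (0.879/0.121) ÷ (0.840/0.160) = 1.38

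The other cuts use the negative binomial tail probabilities in the same way.

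| Cut | m = 3, k = 0.5: P control, P at 1.25m | Odds ratio | m = 5, k = 1: P control, P at 1.25m | Odds ratio |
|---|---|---|---|---|
| ≥1 | 0.840, 0.879 | 1.38 | 0.833, 0.862 | 1.25 |
| ≥4 | 0.337, 0.433 | 1.50 | 0.482, 0.552 | 1.32 |
| ≥7 | 0.106, 0.172 | 1.75 | 0.279, 0.354 | 1.41 |
| ≥10 | 0.030, 0.062 | 2.13 | 0.162, 0.227 | 1.52 |

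The underlying rate ratio is 1.25 in every row.

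**Step 4: saturation of the any-event proportion (for the optional addition).** The formula is the same, with k = 1 and a rate ratio of 1.25.

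- m = 10: 90.9% becomes 92.6%, a ratio of proportions of 0.926/0.909 = 1.02.
- m = 0.1 (rare, as severe events might be): 9.1% becomes 11.1%, a ratio of 0.111/0.091 = 1.22.

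The proportion hides most of a rate difference when events are frequent and very little when they are rare.

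**The case against.** **On the count endpoint.** The mismatch looks like an editing slip. Section 9.4, item 5, says the count analysis was added in an update, and the sentence pointing to Section 4.1.8 suits the two proportions beside it. The endpoint is exploratory, with no test and no p-value, and events per subject can be tabulated without any cut. All of this stands, and it bounds the importance of the point. It does not remove the error: if the sentence is read as covering only the proportions, the count has no stated method at all. A reader might also infer that the endpoint is lost. That goes too far, because one descriptive sentence restores it. The odds ratios above show what a literal reading permits, not what anyone proposes to report.

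**On whole-arm frequency.** The safety objective in Section 1.1 covers "the frequency and severity of the hypoglycemia events with dapagliflozin 5 mg or 10 mg plus adjustable insulin versus placebo plus adjustable insulin", so a reader might infer that the SAP owes an interval estimate against placebo, such as a rate ratio from a count model. The document does not support that:

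- The objective's verb is to assess, where the efficacy objectives say compare.
- Section 4.2.4.4 already reports totals, recurrence categories and exposure-adjusted rates.
- Section 4.2.4.1 deliberately reports adverse events without tests. It does not mention intervals, but leaving them out is consistent with it.

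Rate ratios for up to five groupings (all events and four non-severe classes) and two doses would add up to 5 × 2 = 10 estimates. Two of those classes, probable and relative hypoglycemia, are described in Section 4.2.4.4 as possibly unsuitable outcome measures for evaluating therapy.

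**On the strata.** A reader might infer a demonstrated loss of power in the subgroup tables. The SAP plans no interval there for either measure and gives no event rates, so no such loss can be shown. Severe events are tabulated as their own class and are little affected.

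**Conclusion.** Section 4.2.3.2 is wrong as written on one exploratory endpoint. It sends a per-subject count to a method for binary outcomes, with no cut and no exposure term, and names a dataset that Section 2.1 does not define. This rests on the text alone. The size of the effect, odds ratios of 1.38 to 2.13 or 1.25 to 1.52 for the same rate ratio of 1.25, rests on assumed means and dispersions and illustrates only how much an unplanned cut could matter. No bias is claimed, and no primary or secondary conclusion changes.

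The any-event tables by stratum and HbA1c subgroup contradict nothing in the SAP. They are a weak display for frequent non-severe classes, and improving them is optional.

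**What to change.** **Correct Section 4.2.3.2.** Restrict Section 4.1.8 to the two HbA1c proportions, delete the reference to a randomized-subjects dataset, and add:

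> *For the number of non-severe hypoglycemic events, events per subject (mean, SD, median, range) and the exposure-adjusted event rate will be summarized by treatment group among responders in the Full Analysis Set; no between-group estimate will be given because responder status is defined after randomization.*

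The cost is a wording change and one table. Exploratory objective 12 is then met descriptively, which agrees with the no-testing rule already in that section.

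**Optional, in Section 4.2.4.4.** Next to the any-event proportions by randomization stratum and HbA1c subgroup, also show the number of events and the exposure-adjusted rate by treatment group. The rate is already planned for whole groups, so the added work is small. The price is a few more tables and imprecise rates in small strata. Figures within HbA1c subgroups should stay descriptive, since those subgroups too are formed after randomization.
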